## 19. PUBLICATION POLICY

The CRO and investigators agree to keep strictly confidential all unpublished information and results concerning this trial. Unpublished information must not be published or disclosed without Sponsor's prior written approval. Sponsor reserves all the rights to declare any of its data confidential or of business importance and will provide it only to the regulatory authorities of concern on request/demand.

Publications except for summaries of product characteristics are subject to the written consent of the other party of the contract, which shall not unduly be refused.

Confidential Page 45 of 47

# 21. APPENDIX

# Sample Subject Diary (Protocol CLR\_11\_04)

Confidential Page 47 of 47

1. LIST OF ABBREVIATIONS AND ACRONYMS

Abbreviations and	Description			
Acronyms				
AE	Adverse event			
BUN	Blood urea nitrogen			
C-CASA	Columbia Classification Algorithm of Suicide Assessment			
CI	Confidence interval			
CNS	Central nervous system			
CRO	Contract research organization			
_C-SS RS	Columbia-Suicide Severity Rating Scale			
ECG	Electrocardiogram			
eCRF	Electronic case report form			
ER	Extended release			
GABA	Gamma-aminobutyric acid			
GCP	Good Clinical Practice			
ICH	International Conference on Harmonisation			
MedDRA	Medical dictionary for regulatory activities			
mg	Milligram(s)			
mL	Milliliter(s)			
mm	Millimeter			
MS	Multiple sclerosis			
ng	Nanogram(s)			
PCS	Potentially Clinically Significant			
QC	Quality control			
RBC	Red blood cell			
SAE	Serious adverse event			
SAP	Statistical Analysis Plan			
SDTM	Study Data Tabulation Model			
SOP	Standard operating procedures			
SPARC	Sun Pharma Advanced Research Company			
TEAE	Treatment emergent adverse event			
TLFs	Tables, Listings and Figures			
WBC	White blood cell			

Version 1.0

30Oct2017

2. INTRODUCTION

This Statistical Analysis Plan (SAP) describes the planned statistical analyses to be performed for the analysis of data from Study CLR_11_04, "A Clinical Evaluation of the Safety of When Administered Once Daily to Subjects with Spasticity due to Multiple Sclerosis (MS): An Open Label, Long Term, Safety Trial."

The SAP is prepared to provide a more technical and detailed elaboration of the principal statistical features stated in the protocol. The SAP will ensure that the tables, listings, and figures that will be produced and statistical methods that will be used are complete and accurate and will allow valid conclusions to be drawn. In the development of this SAP, the following documents were used:

- Protocol Number Version 1.0 Amendent 02, 17 Dec 2015
- Electronic Case Report Form (eCRF), 24 Jun 2013

The principles in the following guidance documents are followed in preparation of this SAP:

- International Conference on Harmonisation (ICH) E3 (1995): Structure and Content of Clinical Study Reports
- ICH E6 (1996): Guideline for Good Clinical Practice
- ICH E9 (1998): Statistical Principles for Clinical Trials

In the event that a discrepancy is found between the descriptions in the statistical section of the protocol and this document, the description in this document supersedes the descriptions in the statistical section of the protocol.

The Biostatistician is responsible for updating the SAP throughout the life of the study as needed. The responsible party at SPARC Ltd. will be required to review and approve all versions of the SAP.

Version 1.0

30Oct2017

3. STUDY OVERVIEW

3.1 Study Objectives

This is a clinical study designed to investigate the long term safety of when administered once daily in subjects with spasticity due to multiple sclerosis (MS).

This study is an extension of trial CLR 09 21, which was conducted to demonstrate the efficacy and safety of

This safety trial will enroll subjects from trial

CLR 09 21 as well as subjects who did not participate in that trial

whose spasticity symptoms are stable, as well as subjects with spasticity who have no previous exposure to treatment. Safety data will be collected for at least 26 weeks to examine the long-term safety of

3.1.1 Study Objective

The objective of this study is to investigate the long term safety of when administered once daily to subjects aged 18 years and older.

3.2 Study Design

This is a multicenter, open-label, safety study in subjects with spasticity due to MS. Approximately 550 subjects will be enrolled in approximately 35-40 centers, in order to obtain safety data from at least 250 subjects who have completed at least 26 weeks of treatment and at least 200 subjects who have completed at least 1 year of treatment.

Subjects	enrolled	in clin	ical trial	CLR_(9_21	who co	mplete					
			that	trial wi	ll be e	ligible 1	to partic	ipate ir	this	trial.	In a	addition,
subjects	not enrol	led in	trial CLI	R 09 21	who	are on	a stable	daily	dose			
as well as	S	naïve	subjects	will be	eligibl	e to par	ticipate i	in this 1	rial.			

Informed consent will be obtained from subjects prior to the initiation of any trial-specific procedures.

A Subject Diary (Appendix 1) will be utilized to assess compliance and collect comments regarding any important problems or issues (missed dose, reason for missing dose, disturbing signs/symptoms, etc) associated with this trial. The clinic staff will review the diary during each visit. Comments that may suggest adverse events (AEs) will be reviewed with the subject to determine the presence of AEs. Any missed doses will be recorded in the diary, along with the reason for the missed dose. The diary will help confirm the level of drug compliance in this study.

30Oct2017

Visits are scheduled on: Days -14 (Week -2), 1 (Week 1), 28 (Week 4), 84 (Week 12), 182 (Week 26), and during 3 month interval, follow-up visits.

Table 1 in Section 3.2.3 presents the visit and procedures schedule.

3.2.1 Sample Size Considerations

Approximately 550 subjects will be enrolled, in order to obtain safety data from approximately 250 subjects who have completed at least 26 weeks of treatment and at least 200 subjects who have completed at least 1 year of treatment.

3.2.2 Randomization

No randomization will occur in the study.

3.2.3 Study Assessments Schedules

Study assessments are described in detail in the protocol, and summarized below in Table 1.

Table 1: Visits and Procedures Schedule

	Day -14	Day 1	Day 28	Day 84	Day 182	
Activities	Week -2 Visit 1 (Screen)	Week 1 Visit 2 (Baseline)	Week 4 ± 5 days Visit 3	Week 12 ± 5 days Visit 4	Week 26 ± 5 Days Visit 5 / Premature Termination Visit ^b	Visits Every 3 Months ± 5 days ^c
Informed consent	X	-	-	-	-	
Medical history and demographics	Х	-	-	-	-	
Physical examination	X	-	-	-	X	
Neurologic examination	X	-	-	-	X	
Urine pregnancy test	X	-	X	X	X	X
Vital signs (sitting)	X	-	X	X	X	
Clinical laboratory tests ^d	X	-	-	-	X	
12-lead ECG ^e	X	-	X	X	Xe	
C-SSRS	Xf	-	X	X	X	X
Concomitant medication and physical therapy assessments	X	X	X	X	Х	X
AE evaluation	Xs	Χs	X	X	X	X
Dispense study medication	Xh	X	X	X	X	X
Collect study medication	-	X ⁱ	X	X	X	X
Dispense / collect subject diaries	Xj	Х	X	Х	Х	X
Schedule next visit	X	X	X	X	X	X

^{*}Screening Visit assessments in CLR_11_04 which are identical to final visit assessments in CLR_09_21 do not need to be repeated. The Screening Visit may be completed simultaneously with the final visit for CLR_09_21, and on the following day, if needed, provided drug supply from CLR_09_21 does not run out. Subjects cannot enter CLR_11_04 if drug supply runs out prior to the completion of the screening process.

SAEs recorded for subjects entering from clinical trial CLR 09 21only

For subjects not completing the study, all activities scheduled at this visit are to be conducted during the Premature Termination visit with the exception of the ECG (see footnote "e" below) and the physical and neurologic examinations. These three assessments may be conducted during the Premature Termination visit as needed in order to follow the

Hematology: red blood cell (RBC) count, hemoglobin, total white blood cell (WBC) count, differential WBC count, platelet count; serum chemistry: sodium, potassium, chloride, blood urea nitrogen (BUN), creatinine.

^{*}Completed in triplicate two minute intervals during Visit 5. 12-lead ECG should be performed at the Premature Termination visit, as needed, in order to follow adverse events to resolution

4. STUDY ENDPOINTS AND DEFINITIONS

4.1 Study Safety Endpoints

The study endpoints to be evaluated are safety parameters including:

- Vital signs
- Clinical laboratory results
- 12-lead electrocardiogram (ECG) results
- Physical examination results
- Neurological examination results
- Columbia-Suicide Severity Rating Scale (C-SSRS)
- Treatment Emergent Adverse Events (TEAEs).

4.2 Study Definitions

4.2.1 Study Day

For purposes of describing days on study drug in data listings, data will be assigned a study day, relative to the start of study drug at either Visit 1 or Visit 2, depending on whether they are roll-over subjects or non roll-over subjects. The following rules will be used (this numbering of days differs from the Study Days as described in the protocol):

Roll-over Subjects

For events that occurred after the Visit 1:

Study Day = visit date - date of Visit 1 + 1

For events occurred before study drug administration:

Study Day = visit date - date of Visit 1

Non Roll-over Subjects

For events that occurred after the Visit 2:

Study Day = visit date - date of Visit 2 + 1

For events occurred before study drug administration:

Study Day = visit date - date of Visit 2

Visit numbers as designated on the study eCRFs (Electronic Case Report Forms) will be used. For selected parameters, visit windows will also be calculated for use in descriptive statistics by time.

Version 1.0

30Oct2017

4.2.2 Baseline and Change from Baseline

The baseline time point for different assessments will be defined in the respective sections. For evaluations that are collected at multiple occasions prior to initiation of study treatment, the latest evaluation will be considered the "Baseline" evaluation for analysis.

Unless indicated otherwise, change from baseline (CFB) will be calculated as follows:

• CFB = Value at Visit - Baseline

Percent change from baseline (PCFB) will be calculated as follow:

• PCFB (%) = 100*(Value at Visit - Baseline)/Baseline

5. STATISTICAL ANALYSIS GENERAL CONSIDERATIONS

5.1 Analysis Populations

5.1.1 Safety Population

The safety population will be all subjects who received at least one dose of Baclofen ER Capsules (GRS) during the study and have a subsequent contact with the clinic. Within the Safety Population, the following Safety Groups will be used for all summary and analysis purposes, in addition to an overall summary, derived from the three distinct sources (see Section 5.1.2):

[figure not shown]
- Safety Group 1: Subjects who completed CLR 09 21
- Safety Group 2: Subjects who are on entry
- Safety Group 3: Subjects Entering the Trial with no Prior Treatment

5.1.2 Safety Groups

5.1.2.1 Safety Group 1: Subjects who exited the Study CLR 09 21

Study CLR_11_04 will open for enrollment while study CLR_09_21 is ongoing. Blinded study medication will be temporarily dispensed to all subjects enrolled into CLR_11_04 who have exited study CLR_09_21

All potential subjects will review the informed consent document prior to receiving blinded
study medication kits dispensed via IVRS/IWRS. Kits dispensed will be similar in
appearance and packaging as dispensed during Part 3 of study CLR 09 21.
The actual identity of the contents
can be obtained only by breaking the blinding code.
During Visit 3, and for the remainder of this study, open label kits will be dispensed to all subjects who completed CLR_09_21.
5.1.2.2 Safety Group 2:
Subjects entering the trial complete a Screening period (Visit 1) of up to 14 days to allow all potential subjects to review the informed consent form and complete the procedures At Baseline (Visit 2), these subjects will start with

Subjects receiving other anti-spasticity medications will have the starting dose determined according to the investigator's medical judgment.

5.2 *P*-Values

Data presentations in this safety study will be descriptive. Unless stated otherwise, any significance tests will be two-sided with statistical significance assessed at the alpha (α) 5% level. All p-values will be reported to four decimal places. P-values will not be adjusted to account for multiple comparisons.

5.3 Procedures for Handling Missing Data and Outliers

Every effort will be made to collect all the data and avoid missing data. All missing values will be queried and resolved to the best possible extent. Unless specifically noted otherwise, missing values will not be imputed.

5.4 Interim Analysis

For regulatory purposes, interim reports of safety data accrued will be prepared annually. Post-trial AEs not included in the trial safey database will be included in a separate pharmacovigilance database, which will be used for generating periodic safety reports. No formal interim analyses are planned for the study.

30Oct2017

5.5 Final Reporting and Analysis

All analyses outlined in the protocol and in this SAP will be carried out after:

- The SAP has been approved;
- The study database has been authorized by the study clinical team as complete and final;
- All analysis populations are determined;
- Protocol deviations have been identified.

Any post hoc or unplanned analyses performed and not identified in this SAP will be clearly identified in the CSR.

5.6 Multi-center Studies

There are expected to be approximately 35-40 study sites in this study. Due to the large number of study sites and the small numbers of subjects per site, the analysis of endpoints will not include adjustments for study site.

6. STATISTICAL ANALYSIS METHODOLOGY

All data collected for this study will be presented in summary tables, listings, and figures (TLFs) as indicated in Appendix 1 of this SAP. Shells for TLFs with enough detail for programming will be provided as a guide to develop the programming SAS codes. These shells will be in sufficient detail to simulate the actual TLFs when they are created from the locked database.

Appropriate descriptive statistics will be computed and displayed (by time point and other key variables as appropriate) for both continuous and categorical variables. For continuous variables, descriptive statistics will include n (the number of subjects with non-missing data), mean, standard deviation (SD), 95% confidence intervals, median, minimum and maximum values. For categorical data, the number and percentage of subjects within each category will be presented. The denominator for percentages will be based on the number of subjects with non-missing data appropriate for summary purposes.

Individual data listings of all data represented on the eCRF and from the clinical laboratory will be presented.

6.1 Study Subjects

6.1.1 Subject Disposition

The following descriptive summaries of subject disposition will be provided:

- Number of subjects who were enrolled
- Number and proportion of subjects who discontinued the trial prior to Visit 5 (Week 26)
- Number and proportion of subjects who discontinued for each of the following categories for why a subject may be prematurely discontinued from the trial:
 - o Discontinued Due to Adverse Event: Subjects who are discontinued from the trial medication due to the occurrence of an AE will be recorded as dropouts.
 - o Discontinued Due to Major Protocol Violation: Subjects who are discontinued from the trial due to the occurrence of a major protocol violation will be recorded as dropouts.
 - o Lost to Follow-Up: Subjects available for evaluation in Visit 1, but not evaluated for subsequent visits will be considered as lost to follow-up.
 - O Discontinued Due to Worsening of Condition: Subjects can be prematurely discontinued from the trial due to worsening of condition at the discretion of the investigator.
 - Discontinued Due to Other Reasons: Subjects who are discontinued from the trial due to any other reason will be recorded as dropouts. The reason for discontinuation will be recorded.

A listing of subject disposition will be prepared, inclusive of dates of last dose and last contact, and any investigator comments regarding reason for discontinuation. A summary

table will tabulate overall disposition of the subjects. A figure will diagram the overall disposition of the subjects.

A summary of screen failure subjects will be tabulated by reason for screen failure.

6.1.2 **Demographics**

Descriptive statistics of the safety population will be prepared for the demographic and baseline characteristics listed below, including the numbers, means, standard deviations, medians, minimums, maximums and 95% confidence intervals for continuous variables and the numbers and percentages for categorical variables:

- Age (years)
- Age Group (<65 vs. ≥65)
- Sex
- Race/ethnicity
- Renal function

- Duration of MS (years)
- Type of MS
- Pregnancy prevention status for femal subjects
- Height (cm)
- Weight (kg)
- BMI (kg/m^2)

Listings of individual subject's data will also be produced. A summary table of demographics will be produced with descriptive statistics.

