# 9.6. Withdrawal From the Study

#### 9.6.1. Premature Discontinuation of Subject in the Trial

The investigator will make every effort to keep each subject in the study. However, should a subject be removed from the study or elect to decline further study participation, the information will be recorded on the appropriate page in the eCRF, and the primary reason for discontinuation will be selected: 1) adverse event; 2) major protocol violation; 3) lost to follow-up; 4) worsening of clinical condition or loss of efficacy; or 5) other (for which the reason should be clearly stated).

As far as possible, all assessments and procedures scheduled for the end-of-trial visit must be performed on all subjects who receive trial medication but do not complete the trial according to protocol. The subject must return all unused investigational products.

Subjects who are withdrawn from the trial due to AEs will be treated according to established acceptable medical practice and will be followed for outcome. All pertinent information concerning the outcome of such treatment will be entered in the eCRF.

The investigator will make every effort to contact subjects lost to follow-up.

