#### 12.3.2.1. Subject Disposition Criteria

- Number of subjects who were enrolled
- Number and proportion of subjects who discontinued the trial prior to Visit 5 (Week 26)

Confidential Page 35 of 47

- Number and proportion of subjects who discontinued for each of the following categories for why a subject may be prematurely discontinued from the trial (Section 9.6.1):
  - Discontinued Due to Adverse Event: Subjects who are discontinued from the trial medication due to the occurrence of an AE will be recorded as dropouts.
  - Discontinued Due to Major Protocol Violation: Subjects who are discontinued from the trial due to the occurrence of a major protocol violation will be recorded as dropouts.
  - Lost to Follow-Up: Subjects available for evaluation in Visit 1, but not evaluated for subsequent visits will be considered as lost to follow-up.
  - Discontinued Due to Worsening of Condition: Subjects can be prematurely discontinued from the trial due to worsening of condition at the discretion of the investigator.
  - Discontinued Due to Other Reasons: Subjects who are discontinued from the trial due to any other reason will be recorded as dropouts. The reason for discontinuation will be recorded.

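### Lost to follow-up is worded as seen at Visit 1 only, unlike the eCRF reason in Protocol 9.6.1, and the disposition table and figure are labelled Safety Population although the number enrolled is to be reported

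*SAP*

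**What the plan says.** SAP 6.1.1 (Subject Disposition) lists what will be summarised. The first item is "Number of subjects who were enrolled". The second is the number and share who left before Visit 5 at Week 26. The third is a breakdown by five reasons, in which lost to follow-up reads: "Subjects available for evaluation in Visit 1, but not evaluated for subsequent visits will be considered as lost to follow-up". The last reason is the residual one: "Subjects who are discontinued from the trial due to any other reason will be recorded as dropouts". The section also plans a disposition listing, "inclusive of dates of last dose and last contact, and any investigator comments regarding reason for discontinuation".

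Protocol 12.3.2.1 carries the same list and the same lost-to-follow-up sentence. It introduces the reasons as categories "for why a subject may be prematurely discontinued from the trial (Section 9.6.1"). SAP 6.1.1 repeats the list without that reference.

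Protocol 9.6.1 says that when a subject is removed or declines to continue, "the primary reason for discontinuation will be selected: 1) adverse event; 2) major protocol violation; 3) lost to follow-up", followed by worsening or loss of efficacy, and other. It adds: "The investigator will make every effort to contact subjects lost to follow-up". Neither sentence names a visit.

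SAP Appendix 2 labels both the disposition table (14.1.2) and the disposition figure (14.1.2.1) as Safety Population. SAP 5.1.1 requires at least one dose and a later clinic contact for that population.

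**The concern.** There are two separate defects.

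The first is the wording of the category. What sites record (Protocol 9.6.1) and what the SAP says will be tabulated (6.1.1) are not the same thing. SAP section 2 gives the SAP precedence over the protocol's statistical section. Section 9.6.1 lies outside that section, so both rules stand. Two competent programmers, one working from the SAP sentence and one from the eCRF field, could produce different lost-to-follow-up and other-reason rows from the same data.

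The second is the population of the display. A table confined to subjects with a dose and a later contact cannot account for everyone enrolled. Those it omits include subjects who were given drug and never heard from again, who are themselves early losses.

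In a long-term, open-label safety trial where missing values are in general not imputed (SAP 5.3), the disposition summary is where a reader judges whether losses might conceal tolerability problems. That summary is what is at stake, not the safety tables.

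**Working it through.** The plan states no figure for loss to follow-up, so there is nothing to reproduce and no arithmetic to run. The check is to set the rules side by side.

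**Inputs**
- Category wording: SAP 6.1.1, identical in Protocol 12.3.2.1.
- Recorded reason: Protocol 9.6.1.
- Start of drug: SAP 4.2.1 places it at Visit 1 for roll-over subjects and at Visit 2 for others.
- Safety Population: SAP 5.1.1.
- Table and figure labels: SAP Appendix 2.

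**Step 1. Is the visit limit peculiar to this category?** Of the five reasons in SAP 6.1.1, only lost to follow-up is tied to a visit (1 of 5). The same section counts all discontinuations before Visit 5, and the breakdown by reason has no end point. Subjects last seen at Visit 2 or later therefore need a row.

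**Step 2. Who enters the row?** For a subject who cannot be reached after the last evaluation shown:

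| Last evaluation | Meets the SAP 6.1.1 sentence | eCRF reason available under Protocol 9.6.1 | In the Safety Population |
|---|---|---|---|
| Visit 1, roll-over | Yes | Yes | Only with a dose and a later contact that was not a visit evaluation |
| Visit 1, not roll-over | Yes | Yes | No; drug starts at Visit 2 |
| Visit 2, roll-over | No | Yes | Yes, if dosed |
| Visit 2, not roll-over | No | Yes | Only with a later contact |
| Visit 3, 4, 5 or a three-monthly visit | No | Yes | Yes, if dosed |

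The rows for subjects who did not roll over matter only if such subjects exist. SAP 3.2 and 5.1.1 describe them, but inclusion criterion 6 in Protocol 8.2 requires completion of Part 3 of CLR_09_21 and so does not admit them.

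**Step 3. Consequence of the literal wording.** Within the Safety Population, the row can hold only roll-over subjects dosed from Visit 1 who had some later contact but no later evaluation. It would be empty or nearly so. Every loss from Visit 2 onward fails the sentence and, on that reading, has only the residual category left.

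**Step 4. Population of the display.** SAP 6.1.1 asks for the number enrolled, while Appendix 2 restricts the display to the Safety Population. Subjects who are enrolled but not in the Safety Population are the gap between the two. They remain traceable. SAP 7.4.4 says listings generally include all subjects with data, and Appendix 2 plans Listing 16.2.1.2 (disposition) and Listing 16.2.1.3 (analysis sets) with no population restriction.

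**Step 5. What can change.** Replacing the sentence moves subjects between two rows and leaves the total alone. Changing the displayed population can alter both the denominator and the tabulated number of discontinuations.

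**The case against.** The strongest defence is that the documents already point to a workable reading. Sites must select a primary reason, Protocol 12.3.2.1 presents its categories as those of 9.6.1, and no rule reassigns a recorded loss to other reasons. On that view the Visit 1 sentence is poor drafting, or merely adds subjects seen only once, and programmers will tabulate the eCRF field. This is a reasonable guess at intent, and if it is what happens, the first defect has no effect in practice. What remains is that the SAP drops the reference to 9.6.1 and nowhere says that the eCRF reason governs. A rule that is wrong as written should not depend on a programmer setting it aside.

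On the second defect, the text of 6.1.1 does not itself limit disposition to the Safety Population; only the Appendix 2 titles do. The listings retain everyone, and screen failures have their own table. That is correct, and it limits the point to one table and one figure.

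A reader might infer more than this:
- *That late losses will be reported as other reasons.* The documents do not establish that. It follows only from the literal reading, and the SAP's table shells are not available to settle it.
- *That losses are concealed or the safety results biased.* The listing keeps the dates of last dose and last contact, and no safety table uses this category.
- *That a number of misclassified subjects can be quoted.* No loss rate is given, so any count would be invented.
- *That total discontinuations are untouched throughout.* That holds for the wording change, not for the change of population.

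**Conclusion.** The concern holds as a minor defect with two parts. The lost-to-follow-up sentence in SAP 6.1.1 and Protocol 12.3.2.1 conflicts with the unrestricted eCRF reason in Protocol 9.6.1 and, taken literally, excludes every loss after Visit 2 or later. The disposition table and figure are labelled with a population narrower than the enrolled count that the same section requires.

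The effect is confined to the disposition summary, and its size cannot be stated from the documents. The wording matters only if the rows are programmed from the SAP sentence rather than from the eCRF field. The population matters only if some enrolled subjects lack a dose or a later contact.

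The second part also depends on when a subject counts as enrolled. Protocol 11.1 places enrolment after eligibility is confirmed, and Protocol 10.3 has the entry criteria reviewed at Visit 2, although drug is dispensed at Visit 1 (Protocol 10.2). If enrolment is recorded only at Visit 2, a subject who never returned after Visit 1 would not be counted as enrolled.

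**What to change.** 1. In SAP 6.1.1 and Protocol 12.3.2.1, replace the sentence with: *Lost to follow-up: subjects who discontinue at any time after enrolment with lost to follow-up as the primary reason on the eCRF (Protocol 9.6.1).*
2. Present Table 14.1.2 and Figure 14.1.2.1 for all enrolled subjects, as the single denominator, and change the two titles in Appendix 2. Add one line for the number in the Safety Population and one for enrolled subjects dispensed study drug but not in it. *Dispensed* is the count to use, because without a later contact there may be no confirmation that a dose was taken.

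The Safety Population definition and all safety endpoint tables stay as they are. The cost is one sentence in two places and the population of one table and one figure, using dispensing and disposition data that are already collected. The downside is that the reported loss rate may look less favourable, and that the tabulated discontinuation total and denominator may differ from those on the Safety Population.
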